	
function. These deficits are important for day to day activities.
 
SCI participants with SDB may indeed demonstrate worse cognitive impairment in these domains.
 
More study is needed to determine the full extent of the interaction between SDB and SCI and their combined impact on cognitive function.
	
results between those with and without SDB.
 
b) Additionally, other factors that may impact cognitive performance including pain severity, mood, pre-morbid intelligence, duration of injury, presence of insomnia, and use of sedating medications will be measured and included in a multivariable regression model to better delineate the impact of each of these factors and SDB on cognitive impairment.

1 and 2	
Although there is now some data that demonstrate increased prevalence of poor sleep quality and SDB in SCI subjects, there is no clear evidence that treating these conditions will lead to short and long term benefits.
 
PAP is a medically-justified intervention in persons with SDB, but has seen limited use in persons with SCI. Strength of evidence does not currently support screening for SDB and intervention with PAP in persons with SCI.
 
Persons who are prescribed PAP are not always compliant with its use. Compliance in this population has seen limited study.
 
The impact of PAP on cognitive outcomes in chronic SCI is unknown
 
The impact of PAP on surrogate CV biomarkers, mood, and quality of life in this population is unknown.
	
a) The research will determine the effectiveness of PAP in treating SDB in chronic SCI using gold standard research methodology (RCT).
 
b) The research will provide the empirical support necessary to justify treatment of SDB in persons with SCI.
 
c) The research will examine population-specific compliance levels in PAP use, and identify whether compliance influences health-related outcomes.
 
d) Our clinical trial will identify the impact of PAP therapy on cognitive measures, mood, quality of life, and surrogate CV endpoints. All these measures are relevant to the emotional and physical well-being of participants with chronic SCI and will likely have a practical impact on day to day living in this population.

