### Objectives/Specific Aims/Hypotheses

The proposal describes a multi-center double blinded, placebo controlled randomized trial (RCT) designed to examine the impact of SDB treatment in persons with chronic SCI. The **central hypothesis** is that the treatment of SDB with PAP will improve cognition, sleep quality, HRQOL, and CVD surrogate measures in persons with chronic SCI. The specific aims and hypotheses of the proposed research are:

Specific Aim 1	
Determine the associations between sleep disordered breathing (SDB) and cognitive impairments in chronic SCI and the impact of PAP therapy on cognitive measures in a cohort with chronic SCI and SDB.
 
Hypothesis 1a: Compared with patients without SDB, patients with SDB will exhibit more severe and widespread cognitive impairments (in memory, attention, and executive function), while controlling for depression, pain severity, duration of injury, level of injury, sedative use, and pre-morbid intelligence
 
Hypothesis 1b: SCI participants who are randomized to four months of therapeutic PAP will show improvement in cognitive measures (memory, attention, and executive function) compared with those receiving sham PAP.

Specific Aim 2	
Determine the impact of PAP therapy on surrogate CV biomarkers, sleep quality, quality of life, mood, and pain in a cohort with chronic SCI and SDB.
 
Hypothesis 2a: SCI participants randomized to four months of PAP will show an improvement in CV biomarkers (hs-CRP, TNF-a, VCAM-1, adiponectin, and 8-isoprostanate) compared with sham PAP.
 
Hypothesis 2b: Sleep quality, quality of life, mood, and pain will improve in SCI participants receiving PAP and stay the same or worsen in those randomized to sham PAP.

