## Research Strategy and Study Design

### Study Overview:

During the 4-year study period we will screen 200 SCI participants who meet eligibility criteria and consent to participate with portable level II polysomnography (PSG) and randomize 100 subjects who have SDB to auto-PAP or sham PAP. Participants will be recruited from the University of Miami (Miami Project to Cure Paralysis), the Miami VA, Wayne State University (Michigan Rehabilitation Institute), and affiliated Detroit VA through their outpatient SCI clinics and/or inpatient rehabilitation units. Participants will be asked to complete questionnaires measuring sleep quality (SQ), SDB risk, insomnia severity, daytime sleepiness, pain severity, mood, and HRQOL. They will undergo an overnight, at home (or if hospitalized, in the hospital room) portable unattended PSG performed at their normal sleep time. Subjects with an apnea-hypopnea index (AHI)  $\geq 10$  events/hr will be randomized to receive 4 months of auto-PAP therapy or PAP set at a fixed pressure of 3 cmH20 (sham PAP).

We will perform neuro-psychological evaluations prior to randomization on all participants who complete a portable PSG to evaluate general and pre-morbid function, immediate verbal memory, simple and sustained attention, processing speed, and executive function. Selection of these particular cognitive measures reflects impairments in these domains observed in patients with SDB within the general population. These domains are also impaired in patients with acute and chronic SCI. **Importantly, none of the cited SCI studies have examined the potential role of SDB in cognitive impairment in SCI participants.**

One cognitive measure (PASAT) and 3 sleep questionnaires (PSQI, FOSQ and ESS) will be repeated at 1 month follow-up in those randomized to therapy or placebo. Complete neuro-psychological evaluations will be repeated at the 4 month follow-up time point in those with SDB who were randomized to PAP or sham PAP (primary outcomes). All measures obtained from these repeated assessments will be subject to a Reliable Change Index analysis to control for potential practice effects. We will obtain blood and urine samples for measurement of CV biomarkers at time of randomization and the four month follow-up. Additionally, sleep and quality of life questionnaires will be repeated at four month follow-up (secondary outcomes).

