**Protocol:** [name] will train RAs at both sites to perform a battery of comprehensive, cognitive assessments to obtain a global evaluation of cognitive functioning in all subjects with SCI who undergo PSG. The particular emphasis is on measures related to cognitive impairment common in persons with SDB. Administration of these tests by appropriately trained RAs is consistent with current standards of practice in clinical neuropsychology. Sample protocol sheets and stimuli for each cognitive measure can be found in Appendix 10.

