Prevalence of insomnia will be calculated as the proportion of individuals who complete the AIS with a score  $\geq 6$ . Prevalence of SDB will be calculated as the proportion of individuals who undergo PSG with AHI  $\geq 10/\text{hr}$ .

To determine baseline associations between SDB and cognitive measures (Hypothesis 1a), we will develop Generalized linear models (GLM), with each of the cognitive variables as dependent variables and presence or absence of SDB as an independent variable. The analyses will be repeated with AHI or ODI4 (measures of SDB severity) as independent variables. We will control for other co-variates including age, depression, anxiety, HRQOL, pain severity, duration of injury, level of injury, use of sedating medications, and presence of insomnia. For all GLM developed, the data may be transformed to meet the normality and homogeneity of variance assumptions of the analysis.

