#### Primary Hypothesis (Specific aim 1, Hypothesis 1b)

A test of the primary null hypothesis, that PAP intervention does not increase mean PASAT score against the 1-sided alternative hypothesis that PAP intervention increases mean PASAT, will be based on a general linear model (GLM). PASAT score is modeled as a function of PAP intervention, using an indicator variable with 1 indicating PAP and 0 the sham treatment. A 1 degree of freedom test based on an F statistic will be used to test for a positive coefficient for the PAP indicator. This modeling approach provides a unified framework that accommodates covariates including use of sedating medications, years of education, level of injury, duration of injury, pain severity, presence of anxiety or depression, compliance with PAP, and recruitment center, each of which may reasonably be anticipated to influence PASAT score. We plan to include these covariates in our primary hypothesis test, which will be carried out at  $\alpha = 0.05$ . If the null hypothesis of no effect is rejected, computation of 95% confidence limits on the estimate of treatment difference in PASAT score mean will be carried out.

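### The Hypothesis 1a model names neither recruitment centre nor years of education, which the plan adjusts for in the randomised comparison, and it drops the promised pre-morbid intelligence adjustment

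*Combined protocol and SAP*

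**What the plan says.** The combined protocol and SAP gives the Hypothesis 1a covariates in three places.

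- **Data Analysis, Planned analyses:** "We will control for other co-variates including age, depression, anxiety, HRQOL, pain severity, duration of injury, level of injury, use of sedating medications", with insomnia closing the list. A generalized linear model is fitted to each cognitive variable, with SDB presence as the exposure, and then repeated with AHI or ODI4.
- **Objectives/Specific Aims/Hypotheses:** SDB and no-SDB participants are compared "while controlling for depression, pain severity, duration of injury, level of injury, sedative use, and pre-morbid intelligence".
- **Study Relevance table, Aim 1:** the multivariable regression is to include "other factors that may impact cognitive performance including pain severity, mood, pre-morbid intelligence, duration of injury", with insomnia and sedating medications.

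For the randomised comparison, the Primary Hypothesis section lists sedating medications and then "years of education, level of injury, duration of injury, pain severity, presence of anxiety or depression, compliance with PAP, and recruitment center". Its reason is "each of which may reasonably be anticipated to influence PASAT score", and it states that these covariates will be in the primary test.

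The cognitive tests are given locally: one trainer "will train RAs at both sites to perform a battery of comprehensive, cognitive assessments". Scoring of the cognitive tests and of the PSGs is central, in Miami. The Randomization Protocol expects 100 participants with AHI of at least 10, 50 from each site, randomised 1:1 within centre.

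**The concern.** The plan identifies centre and education as likely determinants of its main cognitive measure. It then names them only in the comparison that needs them less. In Hypothesis 1b, allocation within centre balances centre by design and education in expectation. In Hypothesis 1a nothing balances either: people have SDB or they do not, and the two sites recruit from different sources (a large research-volunteer database and a VA service in Miami, a rehabilitation institute and a VA service in Detroit).

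If the site with more SDB also has lower PASAT scores, part of the site difference is read as an SDB deficit. If it has higher scores, a real deficit is masked. The same holds for education. WRAT-IV Reading would be a partial stand-in for education, but the analysis section leaves it out although the hypothesis itself promises it.

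The gap recurs across every cognitive variable and all three exposures (SDB, AHI, ODI4). Hypothesis 1a is half of Specific Aim 1.

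**Working it through.** **1. The four lists side by side**

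| Covariate | Relevance table (1a) | Aims (1a) | Planned analyses (1a) | Primary model (1b) |
|---|---|---|---|---|
| Recruitment centre | no | no | no | yes |
| Years of education | no | no | no | yes |
| Pre-morbid intelligence | yes | yes | no | no |
| Age | no | no | yes | no |
| Level of injury | no | yes | yes | yes |
| Insomnia | yes | no | yes | no |

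Centre and education are in no 1a list. The three 1a lists also disagree with each other.

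**2. The plan's own figure.** The plan gives no power or sample size for Hypothesis 1a. Its nearest figure is the power of 0.93 for Hypothesis 1b, with 40 per arm, difference 7, SD 9 and alpha 0.05. SE = 9 × √(2/40) = 2.01; 7/2.01 = 3.48; 3.48 − 1.96 = 1.52; power = 0.936 (normal approximation) or 0.930 (t). The figure reproduces as a two-sided calculation, so I use SD 9 below.

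**3. Inputs for Hypothesis 1a.** From the documents: 100 PSG participants per site, SD 9, overall SDB prevalence 0.50, expected SDB cases 50 per site. Assumed, because the documents give no site figures: site prevalences pA and pB, and a PASAT difference D between sites. No true SDB effect is assumed.

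**4. Bias when centre is left out.** The spurious SDB difference is D times the difference between groups in the share coming from site A:

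bias = D × [pA/(pA + pB) − (1 − pA)/(2 − pA − pB)]

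When the prevalences average 0.50 this reduces to D × (pA − pB).

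- pA = pB = 0.50 (the plan's expectation): bias = 0 for any D.
- pA = 0.60, pB = 0.40: bias = 0.2 × D, which is 0.6, 0.8 and 1.0 points for D = 3, 4 and 5.

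**5. False-positive rate.** With 100 SDB and 100 no-SDB participants, SE = 9 × √(2/100) = 1.27. The two-sided 0.05 rejection rate is Φ(bias/SE − 1.96) + Φ(−bias/SE − 1.96):

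| D (assumed) | Bias | Bias/SE | Rejection rate |
|---|---|---|---|
| 3 | 0.6 | 0.47 | 0.076 |
| 4 | 0.8 | 0.63 | 0.096 |
| 5 | 1.0 | 0.79 | 0.123 |

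This ignores the other covariates. With centre in the model, this source of bias is zero in every row.

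**6. Scale.** A bias of 0.6 to 1.0 points is 9 to 14% of the plan's 7-point difference (0.6/7, 1.0/7). The difference detectable with 80% power at 100 versus 100 is about 3.6 points.

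**7. How likely a prevalence gap is.** If the true prevalence is 0.50 at both sites, the SE of the observed gap is √(2 × 0.25/100) = 0.07. A chance gap of one SE with D = 5 gives 0.07 × 5 = 0.35 points and a rejection rate of about 6%. A 20-point gap is almost three such SEs (0.20/0.07 = 2.9), so it would need a real difference between the site populations.

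**8. Education.** The bias would be the PASAT slope per year of education times the group difference in mean years. The documents give neither, so I put no number on it.

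**The case against.** Several points on the other side are sound.

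- **The list is open.** The word including means that centre and education are not pre-specified; it does not exclude them. This stands, but it leaves their inclusion to a choice made after the data are seen.
- **Equal prevalence is expected.** With 50 SDB cases per site the centre bias is exactly zero. This stands as the plan's planning value. It is not a safeguard, and it says nothing about education.
- **Testing is standardised.** PASAT digits are paced by computer, WCST is run by computer, the RAs are trained in common, and scoring is central. These steps reduce site differences in administration. They leave case mix untouched, and central scoring works from what the local examiner recorded. The plan describes computer administration only for PASAT and WCST; SDMT is given orally.
- **Other covariates do some of the work.** Age and the level and duration of injury are in the model, so the unadjusted figures above may overstate the bias.
- **Pre-morbid intelligence may stand in for education.** In part it may, but the analysis section omits it.

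A reader might go further in two ways that the documents do not support. One is to require an inpatient-versus-home covariate, because the sleep study may be done "at home (or if hospitalized, in the hospital room) portable unattended PSG". The plan does not name setting as a PASAT determinant, does not say that cognitive testing takes place in the hospital room, and admits inpatients only after two weeks of recovery. The other is to use the cited SDB prevalence range of 27 to 62% as if it were a gap between these two sites. That range comes from small studies and varies with acuteness and level of injury. Level is already in the model, and every participant here is at least one year post injury.

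**Conclusion.** The gap is real and modest. As written, the Hypothesis 1a model does not name two variables that the plan itself expects to influence PASAT, and it leaves out a third that the hypothesis promises. The centre bias ranges from zero, on the plan's expectation of equal prevalence, to about 0.6 to 1.0 PASAT points with a false-positive rate of about 8 to 12%. The upper figures rest on assumed prevalences of 60% and 40%, an assumed site difference of 3 to 5 points, SD 9, and no adjustment for other covariates. The education bias cannot be sized from the documents.

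A reader might infer that Hypothesis 1a will give a spurious result, or that the trial's main conclusion is at risk. Neither follows. Bias needs a site difference in both SDB prevalence and PASAT, and the documents show neither. The primary PASAT test is randomised within centre, already includes centre and education, and is unaffected.

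**What to change.** Write one Hypothesis 1a covariate list and use it in the Study Relevance table, the Aims and the Planned analyses. Keep the covariates on which the three lists are to agree, and add recruitment centre, years of education and pre-morbid intelligence (WRAT-IV Reading). Apply the list to every 1a model: each cognitive variable, with SDB, AHI and ODI4 as exposure. Fix it before the baseline data are analysed. An inpatient-setting covariate is not required.

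The cost is SAP wording and about three degrees of freedom (one per added variable) out of about 200. No new data collection should be needed: centre is known, WRAT-IV Reading is in the baseline battery for everyone who completes a PSG, and the primary model already needs education. The Baseline Measurements section does not list education by name, and the primary model covers only randomised participants. The sponsor should therefore confirm that education is recorded for those without SDB as well.

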### *A) Prevalence of Sleep Disordered Breathing in Persons with Spinal Cord Injury*

Small cross-sectional studies in persons with SCI report SDB prevalence rates ranging from 27-62%, depending on the acuteness of, and level of injury; **these rates are 2-5 times higher than the general population.** In a longitudinal study of patients with tetraplegia, sleep apnea was present in 60% of subjects within four weeks of injury, reaching a peak incidence of 83% three months after injury. In cross sectional studies conducted by our team, the prevalence of obstructive sleep apnea (OSA-subset of SDB) ranged from 56% in those with incomplete tetraplegia to as high as 91% in those with complete lesions (cited reference and preliminary data). **Given the many health and cognitive consequences related to SDB, it is imperative to determine the health impact of this disorder in the SCI population which is already at risk for many of the same secondary medical complications of SDB (e.g. diabetes, cardiovascular disease, poor memory and concentration).**

**The prevalence of SDB in SCI is considerably higher than general population estimates of 2-4%.** Unfortunately, there is a paucity of information on the underlying reasons for this increased prevalence and more research is needed in this field. Obesity is an important risk factor for SDB. Among the 6 million users of Veteran Health services, an alarming 2/3 of women and 3/4 of men are overweight or obese. A retrospective review of 7959 veterans with SCI reported that 37% were overweight and another 31% obese. Additionally, people with tetraplegia have an increased neck circumference and spend more time sleeping supine, both known risk factors for SDB in the general population. However, these factors do not fully explain the increased prevalence of SDB in persons

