with SCI. In their 2001 retrospective, case-control study of 53 SCI individuals, Burns et al. demonstrated that obstructive sleep apnea in tetraplegia is associated with obesity and a higher cervical cord level but not with ASIA impairment. In 2002, Stockhammer et al. demonstrated that SDB was significantly correlated with age, body mass index (BMI), neck circumference, and time after injury but not with lesion level or ASIA impairment. Berlowitz, et al. have shown that in those with acute tetraplegia, SDB is present at a lower BMI than their non SCI counterparts. This suggests the interplay of several mechanisms that increase the prevalence of SDB in SCI. Interestingly, SCI patients with SDB require significantly less positive airway pressure (PAP) therapy at any given SDB severity compared with able-bodied individuals with sleep apnea.

**Emerging data demonstrates that the prevalence of SDB in SCI is increased. Additionally, the characteristic risks for, and subsequent response to therapy likely differs from the general population and deserves dedicated research to determine the nature and significance of SDB and its treatment in SCI**

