#### *B) Cognitive and Quality of Life Consequences of SDB*

The cognitive functions most frequently and reliably reported as being affected by SDB in the general population, are vigilance, attention, memory, executive and motor functioning. A meta-analytic review suggests that obstructive sleep apnea (OSA) has a moderate to severe impact on vigilance, motor coordination, and executive functions, while there is little effect on intelligence, verbal, and visual-perceptual abilities. Many of the studies are limited by relatively small sample sizes, non-comprehensive cognitive test batteries, and inadequate control groups.

**Cognitive deficits in information-processing, speed, attention, memory, and executive function are also commonly reported post SCI. The intermittent hypoxia and frequently disrupted sleep associated with untreated SDB may worsen already existing cognitive deficits in the subset of patients with both SCI and SDB, leading to sub-optimal cognitive outcomes in this unique patient population. Cardiovascular disease (seen commonly in chronic SCI and in SDB) likely also plays a role in this cognitive decline. Sajkov, et al. studied the effect of SDB on neuropsychological functioning in 37 tetraplegic patients at least 6 months post injury. Thirty percent (11 of 37) had moderate to severe SDB. Neuropsychological measures of cognitive ability were significantly correlated with measures of sleep hypoxia, with deficits cited in attention, concentration, memory and learning. Further, cognitive impairments sustained by subjects with tetraplegia were both statistically and clinically significant when compared with non-disabled population values. These deficits are likely to substantially prolong rehabilitation, reduce future independence, and limit vocational outcomes following injury; all of which are essential benchmarks for successful community re-entry after injury.**

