**Baseline Measurements All Subjects:** At the Miami and Detroit sites the study RA will approach SCI individuals identified by the study PI and Co-investigators to determine eligibility for participation in the study. Upon consent, we will ask participants to complete several questionnaires detailed below. We will schedule participants for a single night unattended portable home PSG within one week of enrollment to evaluate sleep architecture and diagnose SDB. The RA at each site will review medical records to document medical and psychological co-morbidities, medication use, laboratory data, spinal cord injury level, ASIA classification, and duration of injury. We will interview participants during their enrollment visit to obtain a medical/sleep history, and anthropometric measures (height, weight, neck circumference, and abdominal girth at end expiration). Whenever possible the RA or PI/site PI will complete the international SCI core dataset for each participant. Additionally, we will use the international SCI CV function basic data set to obtain information about CV co-morbidity. Cognitive testing will be completed at baseline on all subjects who complete portable PSG. **Figure 2 outlines study flow and measurements.**

We will obtain the following respiratory measures during PSG: a) AHI: defined as the number of apneas and hypopneas per hour of sleep, b) arousal index (AI): the number of arousals per hour of sleep, c) percentage of total sleep time (TST) spent with arterial oxygen saturation (Sa-O2) < 90%, d) mean minimum Sa-O2, and e) oxygen desaturation index 4% (ODI4), defined as the number of four percent desaturation events per hour of study time. Respiratory and sleep architecture definitions will be scored according to accepted criteria put forth by the American Academy of Sleep Medicine (AASM). We will define SDB as an AHI  $\geq 10$ . We will score hypopneas initially using alternative rules (>50% reduction in airflow with 3% desaturation or arousal). We will rescore using recommended rules (>30% reduction in airflow with 4% desaturation). In the sleep research community, there is currently no clear consensus on which scoring method is preferred. SDB prevalence rates reported in the literature differ depending on the definition used. Consequently, we will perform all analyses with both definitions in mind and report any differences in observed associations.

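### Hypothesis 1a compares cognition with and without SDB but names no body-size covariate; BMI should be prespecified in its models

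*Combined protocol and SAP*

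**What the plan says.** Hypothesis 1a (Objectives/Specific Aims/Hypotheses) expects participants with SDB to show more cognitive impairment than those without. SDB status is observed, not assigned. The covariates are named in three places:

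- Data Analysis, planned analyses: "We will control for other co-variates including age, depression, anxiety, HRQOL, pain severity, duration of injury, level of injury", followed by sedating medication and insomnia. The models are then refitted with AHI or ODI4 in place of SDB yes/no.
- The aims: "while controlling for depression, pain severity, duration of injury, level of injury, sedative use, and pre-morbid intelligence".
- The table in Background section G: "other factors that may impact cognitive performance including pain severity, mood, pre-morbid intelligence, duration of injury, presence of insomnia, and use of sedating medications".

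None of the three contains BMI, weight, neck circumference or abdominal girth.

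Elsewhere the document says the following about body size and related factors:

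- Background section A states: "Obesity is an important risk factor for SDB". It cites a study finding that "obstructive sleep apnea in tetraplegia is associated with obesity and a higher cervical cord level", and a second in which SDB correlated with age, BMI, neck circumference and time since injury.
- Background section B says cardiovascular disease (CVD) "likely also plays a role in this cognitive decline".
- Background section E lists obesity among the confounders of the link between SDB and inflammation, and suggests that some null studies did not deal with such confounders adequately.
- Baseline Measurements All Subjects provides for "anthropometric measures (height, weight, neck circumference, and abdominal girth at end expiration" at the enrolment visit, so BMI needs no new data.

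**The concern.** A variable that goes with both exposure and outcome distorts an observational contrast when it is left out. The exposure side is documented here: obesity and BMI go with SDB. The outcome side is only indirect. CVD is said to be a likely contributor to cognitive decline, and Background section C ties low adiponectin to both obesity and CVD.

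The choice of covariates is also uneven. Of the SDB correlates reported by the two studies cited in section A, the analysis section adjusts for age, duration of injury and level of injury. Only the body-size measures are left out.

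At stake are the SDB, AHI and ODI4 coefficients for every cognitive outcome. Section G presents the multivariable model as the means of separating the contribution of SDB from that of other factors, and without a body-size term it cannot do so for obesity.

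**Working it through.** **The plan's own figure.** No sample size or power is given for Hypothesis 1a. The nearest figure is for the randomised comparison: power 0.93 with 40 per arm, a difference of 7 and SD 9. It reproduces at two-sided 0.05 (0.930 by noncentral t, 0.936 by normal approximation). This confirms how the SD of 9 is used.

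**Inputs from the document.** 31% obese (review of veterans with SCI, Background section A); SDB prevalence 0.50 among 200 participants, so about 100 v 100; PASAT SD 9 (sample size paragraph).

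**Assumptions, not in the document.** Obesity-SDB odds ratio 2 to 4; obesity goes with 2 to 4 fewer PASAT points; no other covariates in the model; two-sided 5% test (the plan gives neither level nor sidedness for Hypothesis 1a); no true SDB effect.

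**Step 1: obese share by group.** With equal groups, p1 + p0 = 2 × 0.31 = 0.62. Solve [p1/(1 − p1)] / [p0/(1 − p0)] = odds ratio.

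**Step 2: bias.** Bias = (p1 − p0) × assumed PASAT gap.

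**Step 3: standard error.** SE = 9 × √(2/100) = 1.27.

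**Step 4: false-positive rate.** 1 − Φ(1.96 − bias/SE) + Φ(−1.96 − bias/SE).

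| Odds ratio | p1, p0 | Bias at 2 points (rate) | Bias at 4 points (rate) |
|---|---|---|---|
| 2 | 0.383, 0.237 | 0.29 (5.6%) | 0.58 (7.5%) |
| 3 | 0.423, 0.197 | 0.45 (6.5%) | 0.91 (11.0%) |
| 4 | 0.450, 0.170 | 0.56 (7.2%) | 1.12 (14.2%) |

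For scale, the difference detectable with 80% power at 100 v 100 is (1.96 + 0.84) × 1.27 ≈ 3.6 points.

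**Sensitivity to the assumptions.** Odds ratios of 1.5 to 4 with effects of 1 to 7 points give a bias of 0.09 to 1.96 points and rates of 5.1% to 34%. With continuous BMI (gap between groups 0.3 to 0.8 SD, slope 0.1 to 0.3 outcome SD per SD of BMI), the bias is 0.27 to 2.16 points and the rates 5.5% to 40%.

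**Cost of adjusting.** With equal groups and a BMI gap of d SDs, the variance inflation is 1 + (d/2)². That is 1.02 at d = 0.3 and 1.16 at d = 0.8. The interval widens by √1.02 to √1.16, or about 1% to 8%, before any gain from outcome variance that BMI explains. Power for a 7-point difference stays above 0.999.

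**The case against.** The strongest reply is that the document does not establish confounding. It calls obesity a risk factor for SDB, or reports an association or correlation; it does not call it a cause. It also says that body size and the other recognised factors do not fully explain SDB in this population. No passage links obesity to cognition. The adiponectin statement is a co-association, and section E speaks of inflammation, not cognition. BMI and the sleep study are also obtained at about the same time, at least a year after injury, so their order is not shown. All of this stands. It makes the direction and size of any bias conditional, but does not remove the reason to adjust for a measured factor that the protocol itself ties to the exposure.

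A second reply is that the calculation ignores the planned covariates, which may already carry part of any obesity effect. That also stands, and the table should be read with it in mind.

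A third is that the analysis list is open-ended, so BMI is not excluded. That is true, but an open list leaves the choice until after the data are seen.

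A fourth is that obesity may act through CVD, which Background section C treats as a consequence of SDB. This is a reason for caution in adjusting for CVD. Adjusting for BMI leaves the path from SDB through CVD to cognition open.

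**Conclusion.** The omission is real and consistent across all three covariate lists. If obesity goes with worse cognition beyond what the listed covariates capture, part of that association would be credited to SDB. Under the main assumptions the bias is about 0.3 to 1.1 PASAT points against an SE of 1.27, with a false-positive rate of about 5.6% to 14%. Wider assumptions run from almost no bias to about 2 points. The documents cannot narrow this range, and the upper figures should not be quoted as the expected error.

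A reader might infer three stronger things that the documents do not support:

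- That the protocol calls obesity a cause of SDB. It says risk factor, associated or correlated.
- That the Hypothesis 1a estimates are biased toward the hypothesis. This needs an adverse obesity effect on cognition, which is assumed here.
- That the trial's main result is at risk. The primary inference is the randomised PASAT comparison (Hypothesis 1b), which baseline BMI does not confound.

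This is therefore a lower-priority improvement, worth making because it is nearly free.

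**What to change.** In the Hypothesis 1a paragraph of the planned analyses, prespecify BMI as a continuous covariate, computed from enrolment height and weight. Include it in every model (SDB yes/no, AHI and ODI4, under both hypopnea scoring rules) and for every cognitive outcome. Report the SDB, AHI or ODI4 coefficient with and without BMI, so that readers can see how much depends on it. Add BMI to the lists in the aims and in section G so that all three name it.

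Do not add CVD to the main model. Because the protocol treats it as a consequence of SDB, adjusting for it could remove part of the effect under study; it belongs, if anywhere, in a sensitivity analysis.

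The cost is a short change to the text, no new data, one degree of freedom of about 200 and the modest widening of the interval shown above.
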